7.0 Study Withdrawal/Discontinuation

Taking part in this study is voluntary, and the participant has the right to refuse to take part in the study. The participant can withdraw from the study at any period and should notify the PI or a study staff member. The decision to withdraw will not affect the participant's ability to get healthcare at the institution, or their enrollment in any health plans or benefits. The investigator may decide to discontinue a participant's participation without permission because she may decide that staying in the study will be harmful for the participant, or the sponsor may stop the study. A participant's decision to withdraw from this study will not be retroactive. For example, if a participant provides consent and completes the baseline visit but then decides to withdraw from the study at the post-intervention visit, the data collected from the baseline visit, which was collected in good faith, will not be destroyed.

Criteria for Discontinuation of Individual Participants

Subjects can decide to discontinue entirely from the study at any time for any reason. Subjects can also be discontinued from the study or discontinued from the study treatment due to Investigator decision as detailed below.

1. Withdrawal of consent.
2. At the Investigator's discretion in certain situations such as lack of compliance or serious adverse event.
3. One DKA event or one episode of hyperglycemic, hyperosmolar nonketotic syndrome (HHNS)
4. Dangerous hypoglycemia (glucose <54mg/dl after three treatments or unable to function due to low blood glucose during study visits)
5. Continuous hyperglycemia (random blood glucose >300mg/dl two times in a row during study visits)

Protocol for hypoglycemia

During any study visits, if the study participant develops any of the symptoms below, the study team member will check glucose levels immediately. The symptoms are

- Weakness and tiredness
- Sweating
- Fast breathing
- Shakiness, nervousness, and or anxiety
- Nausea
- Confusion and problems communicating
- Light-headedness, dizziness

If the glucose level is below 70mg/dl, one of the following options will be administered.

1. 2 oz (60ml) juice
2. 15mg of glucose tablets

After 15 minutes, the study team member will re-check glucose level. If the glucose level is still below 70mg/dl, the treatment will be repeated up to 2 times.

If the participant's glucose level is still below 70mg/dl after three treatments, the study team member will notify the PI and ask participants to call healthcare provider. If the participant's glucose level is still below 54mg/dl or the participant is unable to function because of mental or physical changes due to low blood glucose, call 911 immediately and notify the PI.

Protocol for hyperglycemia

During first visit, the finger prick random glucose level of potential participants is 300 mg/dl or higher two times in a row, the RA will notify PI immediately. The potential participants will be informed of their glucose levels and asked to contact their healthcare provider immediately. The PI will withdraw the study participant to prevent severe hyperglycemic events and/or DKA.

Adverse events (AEs) will be reported according to IRB policies. Any adverse event requiring reporting will be reported no later than 10 working days to the IRB using the IRB form "Report of Unanticipated Problem Involving Risk to Participants or Others" (IRB Form #1105). Reporting will depend on adverse event severity:

Grading of Severity

- 0: No AE or within normal limits.
- 1: Mild AE.

- 2: Moderate AE.
- 3: Severe AE resulting in inpatient hospitalization, or a persistent or significant disability/incapacity.
- 4: Life-threatening or disabling AE.
- 5: Fatal AE.

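### The hypoglycaemia procedure gives the glucose-tablet rescue dose in milligrams; as written it is effectively no treatment, and grams were very probably meant.

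*Combined protocol and SAP*

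**What the plan says.** The procedure is in section 7.0, under the protocol for hypoglycemia. It is symptom-driven and limited to visits: "During any study visits, if the study participant develops any of the symptoms below", staff check glucose at once. The treatment rule is "If the glucose level is below 70mg/dl, one of the following options will be administered". The two options are "2 oz (60ml) juice" and "15mg of glucose tablets". Neither is ranked above the other, and either one alone satisfies the rule.

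The follow-up is then set out: "After 15 minutes, the study team member will re-check glucose level", and if the reading is still under 70 mg/dl, "the treatment will be repeated up to 2 times".

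Two later steps count these treatments:

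- Escalation: "If the participant's glucose level is still below 70mg/dl after three treatments, the study team member will notify the PI", and the participant is asked to call a healthcare provider.
- Discontinuation criterion 4, in the same section: "Dangerous hypoglycemia (glucose <54mg/dl after three treatments or unable to function due to low blood glucose during study visits".

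A further sentence calls for the emergency services if glucose is still under 54 mg/dl or if the participant cannot function. It does not say clearly whether the 54 mg/dl trigger waits for three treatments.

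The tablet amount appears only once in the document.

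**The concern.** Fifteen milligrams of glucose is a trace amount, yet it is offered as an equal alternative to a drink of juice. The procedure then treats each dose as a real attempt at rescue, because escalation and one discontinuation criterion both depend on the result after three treatments.

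The clearest case at stake is a participant with symptoms, still functioning, at 54 to 69 mg/dl. If staff follow the tablet line to the letter and repeat it, that person goes through every cycle without effective treatment before anyone senior is told. A participant under 54 mg/dl after three such doses would also meet the glucose part of criterion 4, and so be counted as failing treatments that were not treatments. A participant who cannot function is protected either way, since that triggers an emergency call at once.

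**Working it through.** No sample-size or analysis figure is involved. The check asks whether the written dose could do what the procedure expects of it.

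**Inputs from section 7.0**

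- Dose: 15 mg per treatment by the tablet option.
- Number of treatments: 1 + 2 repeats = 3.
- Total tablet dose: 3 × 15 mg = 45 mg.
- Re-check interval: 15 minutes.
- Thresholds: 70 and 54 mg/dl.

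**Assumption, not in the documents**

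- Blood volume is 4 to 6 L (40 to 60 dl), and all the glucose is absorbed at once and stays in the blood. This gives an upper bound on the direct rise.

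**Direct rise = dose ÷ volume**

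| | 4 L (40 dl) | 6 L (60 dl) |
|---|---|---|
| One dose | 15 ÷ 40 = 0.375 mg/dl | 15 ÷ 60 = 0.25 mg/dl |
| Three doses | 45 ÷ 40 = 1.125 mg/dl | 45 ÷ 60 = 0.75 mg/dl |

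**Rise needed to reach 70 mg/dl**

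- From 69: 70 − 69 = 1 mg/dl.
- From 54: 70 − 54 = 16 mg/dl.

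One dose cannot by itself close even the smallest whole-number gap. Three doses cannot do so for anyone at 54 to 68 mg/dl.

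**Sensitivity to the assumed volume.** With a wider distribution volume of 5 to 20 L, the bounds fall to 15 ÷ 200 = 0.075 up to 15 ÷ 50 = 0.3 mg/dl for one dose, and 45 ÷ 200 = 0.225 up to 45 ÷ 50 = 0.9 mg/dl for three. The conclusion does not depend on the choice.

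**Comparison with the juice option.** Assuming 8 to 15 g of sugar per 100 ml (also not in the documents), 60 ml holds 0.6 × 8 = 4.8 g to 0.6 × 15 = 9 g. That is 4.8 ÷ 0.015 = 320 to 9 ÷ 0.015 = 600 times the written tablet dose. Against 15 g the ratio is 4.8 ÷ 15 = 0.32 to 9 ÷ 15 = 0.60. The two options are of the same order only if the tablet dose is in grams.

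**Time.** Escalation needs a reading after the third treatment, so three cycles take 3 × 15 = 45 minutes. The re-check after the third dose is inferred from the wording of the escalation step. A participant who would have recovered by the first re-check with a real dose would therefore wait up to 45 − 15 = 30 minutes longer, untreated, before escalation. If glucose stays under 54 mg/dl, the emergency call comes at 15 minutes on one reading of the text and at 45 minutes on the other.

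**The case against.** The strongest reply concerns weight, since the error itself is plain.

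- **The harm needs a chain of events.** There must be symptoms during a visit, a reading under 70, a choice of tablets over juice, a literal reading of the unit, and the same choice at each repeat. The text does not forbid switching to juice at the first re-check. This stands: three tablet-only rounds is the worst case. But nothing in the text makes juice the first choice or requires a switch.
- **Low readings at visits should be uncommon.** Section 3 excludes insulin users, section 5.1 requires a reported recent glucose of 80 to 300 before consent and does not ask for an overnight fast, and the visits include no exercise session. This also stands, though other glucose-lowering drugs are not excluded.
- **The 45 minutes is not all due to the error.** A correct dose would follow the same three-cycle schedule. This is right. The unit error adds untreated time only for those who would have responded sooner.
- **The 54 mg/dl ambiguity is a separate drafting point.** That is fair, and it adds nothing to the case for correcting the unit.
- **The intended dose is not documented.** Grams is an inference, and the juice line supports only the order of magnitude.
- **Staff would know what was meant.** Many would. A written rescue procedure should not rely on that, and no step asks a clinician to confirm the dose.

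**Conclusion.** The concern holds. The tablet dose is wrong as written: its direct effect is at most 0.38 mg/dl per dose and 1.13 mg/dl over three, against a shortfall of 1 to 16 mg/dl for a participant at 54 to 69. The exact figures rest on an assumed 4 to 6 L blood volume, but the conclusion is the same up to 20 L. That grams were meant is very likely but remains an inference. A fault in reading the PDF cannot be wholly excluded, although nothing around the line suggests one.

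This should be fixed because it sits in a rescue instruction that staff may act on. Its reach is limited. The documents give no rate of hypoglycaemia at visits, so the number of participants affected cannot be estimated. Section 8.0 planned 24 further participants, each with three in-person visits (two baseline, one post-intervention), so up to 24 × 3 = 72 visits would run under this text. No endpoint, estimate or analysis changes.

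**What to change.** In section 7.0, change the tablet unit from milligrams to grams, so that the line reads 15 g, after the clinical team has confirmed the amount. The same review can confirm that the juice volume is adequate, since under the assumed sugar content it supplies less than 15 g. Notify the study staff, and correct any visit checklist or training sheet that repeats the line.

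The cost is a one-line correction and a short notice to staff. No data collection or analysis needs to change.

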5.4. Post-intervention visit

After 8 weeks, all participants will be invited to an in-person visit (post-intervention visit). During the visit, all the above parameters will be re-measured by the same trained research staff. The visit will take approximately 1 hour including completion of a series of questionnaires (which may be completed by the participants beforehand) and biometric assessments. All participants will wear the activPAL3 and the CGM for 7 days to examine their post-intervention activity and glycemic control. They will return the devices via pre-paid mail. All participants will receive \$50 for the post intervention visit, and an additional \$50 for mailing back the devices to the study team.

Therefore, total compensation would be \$150 for each participant. Also, all participants will be informed of their 24-hour glucose results, and activity patterns retrieved from the ActivPAL device. A subsample of participants from the intervention group will be invited to participate in a separate qualitative exit interview. The one-on-one exit interview will be conducted by the trained study team member during the visit. The interview will last 30 minutes, and each participant will be compensated with \$30 for completing this interview.

1. Questionnaires

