To send weekly text messages from REDCap, we will utilize the third-party service Twilio.com which means that all voice calls and SMS messages will be routed through Twilio's servers. However, REDCap goes to great lengths to ensure that voice call records and SMS transcriptions do not stay in Twilio's logs but are removed shortly after being completed. This is done for security and privacy concerns (e.g., HIPAA), in which our survey participants' phone numbers and their survey responses do not get permanently logged on Twilio's servers but instead remain securely and separately in REDCap. Twilio uses two-factor authentication to access the application administratively. The integrated module can only be turned on by a REDCap Administrator. Twilio configuration is managed by a REDCap administrator. The integration requires 'inspectors' be turned off at the Twilio level to ensure no logging data is retained.

However, this method is limited to have two-way interaction, which means that Twilio and REDCap system do not allow research participants to text back to the study team. To facilitate two-way communications, we will have a wireless cell phone and answer any questions if the participants have any.

All hard copy documents (e.g., sleep diary or wear log) will be stored in a locked filing cabinet and office. All electronic records, including the Master List and voice recordings, will be stored on a secure computer at Vanderbilt University School of Nursing and password-protected, only accessible by the PI and/or her staff. No identifiable information will be stored on any mobile devices (laptops, USB keys, CDs, DVDs, etc.). Research files will be kept for a period of 7 years after the study has been completed. Data entry will be completed in REDCap by the PI and/or her staff and will be imported to SPSS file format for analysis. Only de-identified data will be used for analysis.

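### No systematic adverse-event question is scheduled in the 8 weeks at home, at the post-intervention visit, or after the final mailed-back device wear

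*Combined protocol and SAP*

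**What the plan says.** Section 7.0 describes what happens once an event is known. "Adverse events (AEs) will be reported according to IRB policies", within 10 working days where reporting is required, on a severity scale from 0 to 5. Section 6.0 carries adverse-event reporting in its title, but its content is consent, the risks of each device and of the intervention, and a procedure for severe distress or suicidal ideation.

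Section 7.0 also lists when a participant may be discontinued. Criterion 4 is "Dangerous hypoglycemia (glucose <54mg/dl after three treatments or unable to function due to low blood glucose during study visits" and criterion 5 is "Continuous hyperglycemia (random blood glucose >300mg/dl two times in a row during study visits". Criterion 2 (investigator discretion, including after a serious adverse event), criterion 3 (one DKA or HHNS event) and the clause under which the investigator may act because "she may decide that staying in the study will be harmful for the participant" are not tied to visits.

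After the goal-setting session at Baseline visit 2, Table 3 shows no in-person contact until the end of the intervention: "After 8 weeks, all participants will be invited to an in-person visit (post-intervention visit". Participants then wear the activPAL and CGM for 7 more days, and "They will return the devices via pre-paid mail".

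Between visits, section 5.3.4 describes texts about progress, syncing, goals and encouragement. Section 9.0 says that the "Twilio and REDCap system do not allow research participants to text back to the study team", and offers an alternative: "To facilitate two-way communications, we will have a wireless cell phone and answer any questions if the participants have any".

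**The concern.** Rules for grading and reporting events can act only on events that the team knows about. Participants change their daily activity at home for 8 weeks and are advised to drink 4.5 to 6 bottles of 500 ml a day (2.25 to 3 litres). The protocol says that no sedentary-break program specific to type 2 diabetes exists yet.

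Two things are at stake. First, a fall, a symptomatic glucose episode or a hospital visit at home may come to light too late for the investigator to act on it. Second, a low or zero event count at the end could mean few events or few questions, and the data could not tell these apart. That would limit what the pilot can say about its statements in section 6.0 that fall risk is no more than everyday and that the bottle carries no risk.

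**Working it through.** The plan gives no figure for adverse-event capture, so there is none to reproduce. The check sets each contact from the start of the intervention against one question: does the text have staff ask about adverse events?

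1. **Weekly texts (5.3.4).** Thursday progress feedback, Saturday syncing reminder, Monday summary with a tip and the next goal, and optional encouragement. No adverse-event question.
2. **Weekly SMS survey (5.3.4, step 5).** Three questions that set the next week's sedentary-hour and step goals. No.
3. **Week 4 and week 8 messages (5.3.4).** Monthly sitting hours and a reminder of the overall goal. No.
4. **Study cell phone (9.0).** Participants can raise a problem, but staff do not ask.
5. **Withdrawal (7.0).** The participant should tell the investigator or staff. This is a contact, but no question is specified.
6. **Post-intervention visit (5.4, Tables 2 and 3).** Questionnaires, biometrics, device distribution and feasibility measures. No adverse-event question, but there are indirect prompts: medical history, medication and depressive symptoms again, re-measurement of the earlier parameters, and the distress procedure of section 6.0. A subsample (n=20 in Table 2) is interviewed on topics that include perceived health impacts. None of these is described as asking about falls, injuries or skin and sensor reactions.
7. **Final 7-day wear (5.4).** It begins at the last visit and ends by mail. Section 6.0 lists local infection, bleeding, adhesive irritation and, remotely, a retained fragment as possible sensor harms. No later contact with an adverse-event question is described.

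**Discontinuation criteria against the calendar.** Criterion 5 is limited to study visits. In criterion 4, those words could be read as attaching only to its second half. The first half counts treatments given under the hypoglycemia protocol, however, and that protocol also runs during visits. No visit falls within weeks 1 to 8, and the CGM is worn only for 7 days before and 7 days after the intervention. In that period criteria 4 and 5 have no readings to act on. Criteria 2 and 3 and the harm clause can act, but only if the team hears of the event.

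**Delay in the worst case** (participant does not volunteer the event; the visit takes place as soon as the 8 weeks end):
- As written: 8 weeks × 7 days = 56 days for an event at the start of week 1, and longer if the visit is later or the indirect prompts miss it.
- With an item at weeks 4 and 8, if answered: 4 × 7 = 28 days.
- Total time from the start of the intervention with no scheduled adverse-event question, apart from the indirect prompts at the visit: 56 + 7 = 63 days.

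**The case against.** The strongest reply is that the plan is not silent on safety and that the exposure is mild. Insulin users, people with random glucose above 300, unstable patients and those with kidney disease that limits water intake are excluded. Diabetes treatment is unchanged, and the activity is short bouts of standing or walking. Participants are in touch with the study every week, can call the study phone, and are to notify the team if they withdraw. Section 5.4 also promises them their glucose and activity results, which may mean a contact after the devices come back. The same device types are worn first at baseline with in-person return, so an early skin reaction can be seen there. All of this stands and keeps the point minor. It does not supply the question itself.

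A reader might infer that events can reach the team only if volunteered. The documents do not support that for the post-intervention visit, where the indirect prompts apply to everyone and the interview to some. A reader might also infer that a reported event between visits has no stopping route. That is wrong too, because criteria 2 and 3 and the harm clause apply at any time.

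It is also fair to object that text-message content is what the study is iterating and that replies to goal texts are a compliance measure in Table 2. A set of health questions inside the weekly survey could disturb both. That objection stands and shapes the fix.

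**Conclusion.** The point holds, and its severity is minor. In the visible text, no systematic adverse-event question is scheduled in the 8 weeks at home, at the post-intervention visit, or after the final wear. Apart from the indirect prompts at that visit, learning of an event depends on the participant volunteering it. The practical size is a possible delay of 56 days or more for a week-1 event. The 56 days is the extreme case of no disclosure, not a typical delay.

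The number of events missed cannot be computed, because the documents give neither an event rate nor the share of participants who would report unprompted. The conclusion also rests on what could be read. The text-message examples and interview guide are in appendices that were not seen, and the consent pages were removed. Any of these may ask participants to report problems, which would narrow the gap.

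**What to change.** Write one short fixed adverse-event question covering falls or injury, symptomatic low or high glucose, DKA or HHNS, emergency or hospital visits, and skin or sensor reactions. Ask it of every participant:

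- at the post-intervention visit;
- at the contact when a participant withdraws;
- on a one-line slip returned with the mailed devices.

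Add one yes/no health-problem item, with the study phone number for urgent problems, to the existing week 4 and week 8 messages. Keep it separate from the goal-reply survey so that the compliance measure is unaffected. Test beforehand that replies arrive: section 5.3.4 describes messages going both ways, while section 9.0 says participants cannot text the team back.

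State that events reported between visits prompt investigator review under criteria 2 to 5, and name the role that reads the replies and how soon. Report events together with the number of participants asked.

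The cost is a small extra burden on participants, staff time to review replies, and some false alarms to sort. No visits or devices are added.

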8.0 Statistical Considerations

Sample Size Calculation

Because this is a novel intervention, we cannot use an exact effect size from the literature. As of today (May 22), we have recruited 16 participants; 3 have withdrawn, 5 randomized into intervention group, 8 assigned to control group. For the remaining iterative process, each cohort will have 10 participants. It will give us enough power to be saturated in terms of qualitative findings. Assuming a 15% attrition rate, we plan to enroll 24 more participants, for a total of 40 participants.

Analysis Strategies

Aim 1: Feasibility and acceptability outcomes will be reported as percentages or averages. For the exit interview, we will collaborate with the Vanderbilt Qualitative Research Core in developing a semi-structured interview guide and thematic analysis. To enhance credibility, we will follow the consolidated criteria for reporting qualitative research (COREQ) guidelines.⁴⁴

Aims 2 & 3: Descriptive analyses are planned to characterize the study sample on all measures including baseline demographics and covariates. For this pilot study, exploratory linear mixed modeling will be used to provide descriptive statistics relative to treatment effects, both within- and between-groups effects on the primary and secondary outcomes over time. We will also estimate effect sizes for those outcomes.

Exit Interview

We will develop a semi-structured interview guide and thematic analysis. The exit interview will be audio recorded, transcribed verbatim, and analyzed using a thematic approach to guide refinements to future SB reduction interventions as well as identify barriers and facilitators to SB reduction. To enhance credibility, we will ensure methodological triangulation (audio recording, surveys, and field notes), audit trail and peer-debriefing process.⁴⁵

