5.0 Study Procedures

This iterative design process requires multiple cohorts until reaching the general agreement in terms of participants' satisfaction and feedback on the intervention. Below is the steps to iterative process of developing Sit Less Program.

As of today (May 15, 2023), we are currently undergoing the first phase, testing Sit Less V1 and will collect participants' feedback in June 2023. We also collected user's feedback from a sibling study " Reducing sedentary time in patients with cardiovascular disease: A pilot randomized controlled trial (Sit Less Study)" IRB # 220416. This sibling study has the same intervention components and is now undergoing qualitative analysis based on intervention group participants' feedback.

35

Below is a detailed study process over time for all of cohort participants.

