5.3. Intervention

The 8-week intervention will consist of four components. All study subjects will be assigned to intervention group. After the intervention, the study subjects will keep their Fitbit and the HidrateSpark smart water bottle.

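### Section 8.0 plans between-group treatment effects, but Section 5.3 puts everyone on the intervention; the only controls are 8 early recruits, so no controlled effect is available for the 24 later participants

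*Combined protocol and SAP*

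**What the plan says.** Section 8.0, Analysis Strategies, states for Aims 2 and 3 that "exploratory linear mixed modeling will be used to provide descriptive statistics" and that these will be "relative to treatment effects, both within- and between-groups effects on the primary and secondary outcomes over time". Effect sizes for those outcomes are to be estimated as well. Aim 2 (Section 2.0) concerns preliminary efficacy on change in sedentary time and prolonged bouts.

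Section 5.3 describes allocation in one sentence: "All study subjects will be assigned to intervention group".

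The sample size paragraph of Section 8.0 reports that of 16 people recruited by May 22, "3 have withdrawn, 5 randomized into intervention group, 8 assigned to control group". It goes on: "For the remaining iterative process, each cohort will have 10 participants", and "Assuming a 15% attrition rate, we plan to enroll 24 more participants, for a total of 40 participants".

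Section 5.0 says "This iterative design process requires multiple cohorts until reaching the general agreement" and announces the stages with "Below is the steps to iterative process of developing Sit Less Program", but those stages are not readable in the text available. It then introduces a single study process for every cohort. Section 2.0 says the frequency and content of the text messages will be refined as the study proceeds. Section 5.4 draws exit interviewees from the intervention group, which also implies a second group.

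**The concern.** A study in which everyone receives the intervention has no between-group treatment effect. One is planned here, and the only people it could be measured against are the 8 early controls. The readable text does not say what they received, how they were allocated, whether they are analysed, or whether they later receive the intervention.

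Three contrasts fit the word groups: the early 5 v 8; all intervention participants against those 8; and one cohort or program version against another. They answer different questions and have different precision. The first two are about intervention against control, and the third is about versions. No model terms are listed, so the plan neither includes nor excludes a cohort term that would tell the first two apart.

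Aim 2 is the efficacy aim, so whichever contrast is used becomes its result. If the choice waits until the data are in, an effect size called a treatment effect could go into planning a later trial when it is really a pre-post change or a mostly non-concurrent comparison.

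**Working it through.** **The plan's counts.** 3 + 5 + 8 = 16 recruited, and 16 + 24 = 40 in total. If two cohorts of 10 remain (an assumption; the number of cohorts is not given), 20/(1 − 0.15) = 23.5, rounded up to 24. The figures are consistent. They rest on qualitative saturation, so there is no powered comparison to reproduce.

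**Who could contribute.**
- Intervention, controls not crossing over: 5 + 24 = 29 enrolled, of whom 24/29 = 83% are later enrolments.
- Intervention, controls crossing over: 5 + 8 + 24 = 37 enrolled.
- Later completers at 15% attrition: 24 × 0.85 = 20.4, about 20.
- Completers if all 13 early participants finish: 5 + 20 = 25 without crossover, and 25 + 8 = 33 with it.

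**Precision.** Unit: SD of within-person change, assumed equal across groups. Two-sample 95% half-width = t(0.975, n1 + n2 − 2) × √(1/n1 + 1/n2). Pre-post half-width = t(0.975, n − 1)/√n.

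| Estimate | Calculation | Half-width (SD) |
|---|---|---|
| Early intervention v control, 5 v 8 | 2.201 × 0.570 | 1.25 |
| All intervention v early controls, 25 v 8 | 2.040 × 0.406 | 0.83 |
| Cohort v cohort, 10 v 10 | 2.101 × 0.447 | 0.94 |
| Pre-post, 25 completers | 2.064/5 | 0.41 |
| Pre-post, 33 completers | 2.037/5.745 | 0.35 |

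The narrowest intervention-v-control interval is the 25 v 8, and most of its intervention side enrolled later.

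**What later cohorts do to a pooled figure (illustrative).** Suppose later cohorts differ in mean change by d for reasons unrelated to the intervention, and no cohort term is fitted. Later participants are 20 of the 25 completers, so the pooled intervention mean moves by (20/25)d = 0.80d. The 25 v 8 contrast moves by the same amount. The documents give no value for d. Assuming 0.25 and 0.5 SD, the shift is 0.20 and 0.40 SD.

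The pooled pre-post mean moves by the same 0.80d, and its interval is narrower. Simulation with normal data, equal SDs, 5 + 20 intervention and 8 controls gives this coverage of nominal 95% intervals:

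| d (assumed) | 25 v 8 contrast, covering the true effect | Pooled pre-post, covering the first-cohort change |
|---|---|---|
| 0 | 95% | 95% |
| 0.25 SD | 92% | 84% |
| 0.5 SD | 85% | 53% |

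Pooled pre-post change is therefore no safer a measure of what the first version did. It averages over cohorts and versions and has no comparator, and it has to be described that way.

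**The case against.** **Sections 5.3 and 8.0 may describe different periods.** Section 5.3 looks ahead, while the 5 and the 8 are reported as past recruitment, so the between-group phrase may refer only to the early participants. That is possible. But Section 5.3 speaks of all subjects, the 8 controls are inside the total of 40, and nothing confines the between-group analysis to the early participants. The wording still needs reconciling.

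**Text may have been lost.** The stages announced in Section 5.0 cannot be read here and may define cohorts. This stands: a reader should not conclude that the plan never defines cohorts or versions. Such a definition would still not reconcile Section 5.3 with a between-group treatment effect, nor supply controls for later enrolments.

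**Pooling against the 8 is not proposed.** A reader might infer that the sponsor intends to compare all intervention participants with the early controls. No passage says so. The 0.80d shift and the coverage figures illustrate one reading with an assumed d; they do not measure a defect in a stated analysis.

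**The early comparison may not be randomized or concurrent.** A reader might take the 5 v 8 as a small randomized trial. The text uses randomized for the 5 and assigned for the 8, and does not say they were allocated over the same period. Neither label can be used until this is settled.

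**This is a pilot.** The modelling is already called exploratory and descriptive, and the sample size rests on qualitative saturation. That answers any complaint about power or a missing test, and none is made here. A descriptive estimate still needs a defined contrast and an accurate name.

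**Conclusion.** The point holds in a limited form and should be fixed. Section 5.3 conflicts with the between-group treatment effects and effect sizes of Section 8.0. The only controls are 8 early recruits, so the design going forward gives no controlled effect for the 24 later participants. What is available is an early 5 v 8 contrast, with a half-width of about 1.25 SD if all 13 finish, and an uncontrolled pre-post change, with a half-width of about 0.41 SD for 25 completers or 0.35 SD for 33.

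These figures assume equal SDs, 15% attrition among later enrolments and none among the 13. The cohort-shift figures also rest on an assumed d. Confidence is medium, because part of Section 5.0 cannot be read. Two stronger conclusions are not supported: that the plan has chosen a biased pooled comparison, and that pre-post change avoids the cohort problem.

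**What to change.** (a) Reconcile Section 5.3 with Section 8.0. State what groups means, how the 8 controls were allocated, and whether they later receive the intervention.

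(b) Make within-person pre-post change with a 95% CI the main Aims 2 and 3 estimate, by cohort or version first and then pooled. Call it uncontrolled pre-post change, not a treatment effect, and note that the pooled value averages over versions.

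(c) Limit any intervention-v-control effect size to the early 5 v 8. Call it randomized or concurrent only if (a) confirms it. Label any contrast that adds later cohorts as a non-concurrent sensitivity analysis, and any between-cohort contrast as a comparison of versions.

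(d) Beside the total of 40, state how many contribute to the pre-post estimate: up to 29 enrolled without crossover, up to 37 with it.

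The cost is rewording of Sections 5.3 and 8.0, with no new data. The downside is a visibly wide early contrast and no controlled effect size for later versions.
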